#### **10.5.4 Overall survival (OS)**

The overall survival (OS) following first line treatment with Everolimus + Letrozole is defined as the time from the date enrollment to date of death due to any cause. The OS analysis will be performed 24 months after the last patient's recruitment. If a death has not been observed by the date of analysis cutoff, then OS will be censored at the date of last contact. The analysis for OS will be based on the data from FAS. The median OS as well as the 25th and 75th quartile will be estimated using the Kaplan-Meier method and presented along with 95% confidence intervals.

#### **10.5.5 Other secondary objective**

##### **10.5.5.1 Therapeutic intervention for stomatitis**

The secondary objective, to evaluate a therapeutic intervention to reduce the severity and duration of stomatitis, will be performed using the PRO questionnaire OSDQ data from patients in FAS who had an incidence of stomatitis while on study and were enrolled in countries where the alcohol-free 0.5mg/5ml dexamethasone oral solution is commercially available. The analysis for this objective will be based on PRO data for the first incidence of

stomatitis AE. The mean, standard deviation and 95% confidence interval of each severity items in the questionnaire will be calculated at each day for the two therapeutic interventions for stomatitis groups and presented graphically. The duration of the first stomatitis incidence will be calculated using the dates reported in the PRO, the median duration with 95% confidence interval of the first stomatitis AE will be estimated using Kaplan-Meier method for the two therapeutic interventions for stomatitis groups. As supportive analysis, the median duration will also be estimated using the duration calculated from start dates and end dates reported in AE CRFs.

As an exploratory analysis, sensitivity analysis for duration and severity may be performed on PRO data from multiple occurrences on the same patient. In this analysis appropriate methods will be used to account for within patient correlation.

The PRO will be not be administered during the Extension Phase.

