### **2.2.1 Stomatitis therapeutic intervention**

Stomatitis, the inflammation of mucous membranes lining the mouth and throat, has been observed in approximately 44-64% of everolimus-treated patients (Afinitor PI). It is also a common adverse event associated with radiation and chemotherapy. Specific strategies to prevent and/or ameliorate the severity of everolimus-associated mucositis are not well documented. Caphosol is an oral mouth rinse indicated as an adjunct to standard oral care in the prevention and treatment of stomatitis caused by radiation or high dose chemotherapy. Low level laser therapy (LLLT) has also been suggested by the Multinational Association of Supportive Care in Cancer (MASCC) and the International Society for Oral Oncology (ISOO) to reduce the incidence of oral stomatitis and its associated pain in patients receiving high dose chemotherapy or chemo-radiotherapy ([Keefe et al 2007](#)). However, mTOR inhibitor-induced stomatitis is a different clinical entity, manifesting more frequently as discrete aphthous-like lesions rather than diffuse inflammation. A recent study evaluated the clinical presentation and management of stomatitis in 17 patients treated with an mTOR inhibitor. The majority of patients were treated with topical corticosteroids including an oral dexamethasone solution which was rinsed and expectorated. Clinical improvement was noted in over 85% of topical corticosteroid-treated patients ([de Oliveira et al 2011](#)). Additional reports from investigators indicate that an oral steroid rinse may help to ameliorate mTOR-induced stomatitis ([name], personal communication, February, 2012 and [name], personal communication, March 2012).

As a secondary endpoint, this trial will assess the effectiveness of treating stomatitis using an alcohol-free 0.5mg/5ml dexamethasone mouth rinse in countries where the solution is commercially available. At the onset of symptoms, enrolled patients will contact their physician. Based on preliminary confirmation of diagnosis, patients will be asked to visit the study site within 24 hours. Upon confirmation of the diagnosis of stomatitis the patient will be

randomly assigned to use either 0.5mg/5ml dexamethasone mouth rinse swished and expectorated 3 times per day or the standard of care normally used to treat stomatitis at the patient's center.

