### **6.2.2.1 Management of stomatitis/oral mucositis/mouth ulcers**

Patients with a clinical history of stomatitis/mucositis/mouth ulcers and those with gastrointestinal morbidity associated with mouth/dental infections, irritation of esophageal mucosa e.g. gastroesophageal reflux disease (GERD) and pre-existing stomatitis/mucositis must be monitored even more closely. Patients should be instructed to report the first onset of buccal mucosa irritation/reddening to their study physician immediately.

Stomatitis/oral mucositis/mouth ulcers due to study drug should be treated using local supportive care. Please note that investigators in earlier trials have described the oral toxicities associated with everolimus as mouth ulcers, rather than mucositis or stomatitis. If examination reveals mouth ulcers rather than a more general inflammation of the mouth, please classify the adverse event as such. As noted in [Section 6.1](#), patients in countries where the alcohol-free 0.5mg/5ml dexamethasone oral solution is commercially available, randomized to dexamethasone will be prescribed a 0.5mg/5ml dexamethasone mouth rinse to swish and

expectorate 3 times per day. Treatment of stomatitis/oral mucositis/mouth ulcers for patients randomized to standard of care may include the following measures in conjunction with institutional standards:

1. For mild toxicity (grade 1), use conservative measures such as non-alcoholic mouth wash or salt water (0.9%) mouth wash several times a day until resolution.
2. For more severe toxicity (grade 2 in which case patients have pain but are able to maintain adequate oral alimentation, or grade 3 in which case patients cannot maintain adequate oral alimentation), the suggested treatments are topical analgesic mouth treatments (i.e., local anesthetics such as benzocaine, butyl aminobenzoate, tetracaine hydrochloride, menthol, or phenol) with or without topical corticosteroids, such as triamcinolone oral paste 0.1% (Kenalog in Orabase®).
3. Agents containing alcohol, hydrogen peroxide, iodine, and thyme derivatives may tend to worsen mouth ulcers. It is preferable to avoid these agents.

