## **8 Safety monitoring and reporting**

### **8.1 Adverse events**

#### **8.1.1 Definitions and reporting**

An adverse event is defined as the appearance of (or worsening of any pre-existing) undesirable sign(s), symptom(s), or medical condition(s) that occur after patient's signed informed consent has been obtained. Please refer to [Section 6.1](#) for the protocol specific definition of study treatment.

Abnormal laboratory values or test results occurring after informed consent constitute adverse events only if they induce clinical signs or symptoms, are considered clinically significant, require therapy (e.g., hematologic abnormality that requires transfusion or hematological stem cell support), or require changes in study medication(s).

Except for screening failures, adverse events that begin or worsen after informed consent should be recorded in the Adverse Events CRF. Conditions that were already present at the time of informed consent should be recorded in the Relevant Medical History/Current Medical Conditions of the patient's CRF. Adverse event monitoring should be continued for at least 28 days following the last dose of study treatment. Adverse events (including lab abnormalities that constitute AEs) should be described using a diagnosis whenever possible, rather than individual underlying signs and symptoms. When a clear diagnosis cannot be identified, each sign or symptom should be reported as a separate Adverse Event. Adverse events will be assessed according to the Common Terminology Criteria for Adverse Events (CTCAE) version 4.0.

If CTCAE grading does not exist for an adverse event, the severity of mild, moderate, severe, and life-threatening, corresponding to Grades 1 - 4, will be used. CTCAE Grade 5 (death) will not be used in this study; rather, information about deaths will be collected through End of Treatment eCRF, Study Evaluation Completion eCRF and/or Survival information.

The occurrence of adverse events should be sought by non-directive questioning of the patient (subject) during the screening process after signing informed consent and at each visit during the study. Adverse events also may be detected when they are volunteered by the patient (subject) during the screening process or between visits, or through physical examination, laboratory test, or other assessments. As far as possible, each adverse event should be evaluated to determine:

1. The severity grade (CTCAE Grade 1-4)

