## **10.1 Analysis sets**

### **10.1.1 Full Analysis Set**

The primary efficacy population is defined as the Full Analysis Set (FAS), which consists of all patients to whom the first line study treatment has been assigned. All primary efficacy analyses will be evaluated based on data from this population.

For second line efficacy analyses a subset of the FAS will be used and referred to as Full Analysis Set 2nd line (FAS-2L), which consists of all patients in the FAS who received at least one dose of 2nd line study medication.

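### Section 10.5.5.1 selects the stomatitis comparison by a recorded stomatitis event rather than by randomization, while 6.2.2.1 has mouth ulcers recorded as a separate event

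*Protocol*

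**What the plan says.** Protocol section 10.5.5.1 bases the stomatitis objective on data obtained "using the PRO questionnaire OSDQ data from patients in FAS who had an incidence of stomatitis while on study", restricted to countries where the alcohol-free solution is commercially available. The episode is fixed next: "The analysis for this objective will be based on PRO data for the first incidence of" a stomatitis adverse event. Daily item means are then given "for the two therapeutic interventions for stomatitis groups and presented graphically". The duration of that episode is estimated by Kaplan-Meier in each group from the questionnaire dates. A supportive estimate uses the start and end dates on the adverse event CRF.

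The two groups come from the 1:1 randomization in section 6.3.2, made once stomatitis is diagnosed.

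Section 6.2.2.1 handles stomatitis, oral mucositis and mouth ulcers together, and it describes care for all three in patients randomized to standard of care. On recording, however, it says: "If examination reveals mouth ulcers rather than a more general inflammation of the mouth, please classify the adverse event as such".

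Section 2.2.1 describes stomatitis from this drug class as "manifesting more frequently as discrete aphthous-like lesions rather than diffuse inflammation". The introduction to the Oral Stomatitis Daily Questionnaire (OSDQ) in Appendix 1 counts mouth ulcers as part of the soreness being rated.

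**The concern.** Randomization and the questionnaire use a broad concept of stomatitis that includes ulcers. Adverse event recording splits that concept. The analysis rule then refers to a stomatitis adverse event and provides no way to bring the split terms back together. A site that follows every instruction can randomize a patient, collect her OSDQ and record mouth ulcers. Taken at its word, section 10.5.5.1 then finds no qualifying event for her.

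The comparison is interpretable because of the random assignment. If the event term decides who is in the set or which episode counts, the groups may no longer be those that were randomized. The term may also be recorded after the assignment is known, since section 6.3.3 states that the trial is open-label. With few patients randomized, a handful of such cases would matter.

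**Working it through.** The protocol states no sample size, effect size or test for this comparison (section 10.8 concerns first-line PFS only), so there is no figure to reproduce. The check is of the text, followed by a sense of scale.

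**1. Which condition can remove a randomized patient?**
- FAS membership: none. Section 10.1.1 defines the FAS as the set "which consists of all patients to whom the first line study treatment has been assigned", and every sub-study patient comes from it.
- Country: none. Section 6.3.2 randomizes only where the solution is available.
- A stomatitis incidence, and a first stomatitis adverse event: possibly, depending on the recorded term.

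The event term is therefore the only condition of the three that can exclude a randomized patient.

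**2. What happens to each kind of patient under a literal reading?**

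| Situation | Result under 10.5.5.1 |
|---|---|
| Randomized at first onset, recorded as stomatitis | Randomized episode analysed, as intended |
| Randomized, recorded as mouth ulcers, no later stomatitis event | No qualifying event |
| Randomized, recorded as mouth ulcers, later event recorded as stomatitis | The later event becomes the first stomatitis event |
| Mild stomatitis noted only at a later visit and never confirmed or randomized, then a randomized episode | First event precedes randomization |

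In the third row the patient keeps her assigned mouth treatment (section 4.1). The later episode nevertheless follows earlier exposure to that treatment, and possibly an everolimus interruption or reduction under Table 6-10. It is not the episode for which she was randomized.

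The fourth row is conceivable because section 8.1.1 says that adverse events "should be sought by non-directive questioning of the patient" at visits, which can reveal an episode after it has passed.

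**3. Which analysis is exposed?**
- OSDQ severity and duration: section 7.2.6 hands out the first booklet when the site confirms the diagnosis. In solution countries the same confirmation leads to randomization. An unconfirmed episode (row four) should have no booklet. Rows two and three can still affect these analyses if the first stomatitis event is used to select the OSDQ data.
- Adverse event CRF duration: this rests directly on the recorded event and its dates, so rows two, three and four all apply.

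**4. Scale.** The Amendment 4 rationale reports 20 patients randomized. The share f recorded as mouth ulcers is not given, so 0%, 25% and 50% are assumed. The number left is n = 20 × (1 − f). With equal groups of n/2, an approximate 95% half-width for a difference in means, in standard deviation units, is 1.96 × √(2/n + 2/n) = 1.96 × √(4/n).

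| f (assumed) | n | Half-width |
|---|---|---|
| 0% | 20 | 1.96 × √0.200 = 0.88 SD |
| 25% | 15 | 1.96 × √0.267 = 1.01 SD |
| 50% | 10 | 1.96 × √0.400 = 1.24 SD |

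The protocol plans estimates by group rather than a difference, so the half-widths only indicate scale.

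**The case against.** The strongest reply is that the plan works when followed in its evident sense. Patients contact the site at first onset and are randomized on confirmation, so the first episode is the randomized one. The main analyses use questionnaire data tied to that same confirmation. Section 10.5.5.1 names no preferred term, and the protocol elsewhere uses stomatitis broadly enough to cover aphthous-like lesions. Section 10.5.5.2.1 allows related terms to be regrouped, and an analysis plan that is not shown could do so.

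Much of this stands. It limits the point to a literal reading and puts most of the exposure on a supportive analysis. It does not remove the conflict. Section 6.2.2.1 explicitly asks for ulcers to be recorded separately, section 10.5.5.1 refers to a stomatitis adverse event, and the regrouping option is discretionary and sits in the safety section. An analysis plan that grouped the terms would be repairing a stated rule, not filling in detail.

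Three stronger readings are tempting but not supported:
- A reader might infer that using the FAS drops randomized patients. It drops none.
- A reader might infer that unrandomized episodes enter the comparison and dilute it. That is only a possibility. A patient who was never randomized has no assigned group, and an unconfirmed episode should have no booklet. Nor does 20 randomized out of 202 enrolled prove the inference. Section 2.2.1's 44–64% incidence gives 89 to 129 expected cases overall (202 × 0.44 and 202 × 0.64), but enrolment in solution countries is not given. Twenty would fit about 31 to 45 patients there (20/0.64 and 20/0.44).
- A reader might turn the description in section 2.2.1 into a loss of a third to a half of the randomized patients. Clinical appearance is not a recording rate, and the documents give none.

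**Conclusion.** The point holds as a conflict between two stated rules. Section 10.5.5.1 ties the set and the episode to a stomatitis event and not to randomization, while section 6.2.2.1 diverts mouth ulcers to another event. A patient randomized for ulcers can lose her qualifying event or have a later episode analysed in place of the randomized one. The adverse event CRF duration is most exposed and the OSDQ analyses less so.

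This rests on reading stomatitis in section 10.5.5.1 as the recorded event, and on sites following the instruction in section 6.2.2.1. The number affected is unknown. The range of 20, 15 or 10 patients depends on the assumed shares and on the Amendment 4 count, which may have risen afterwards. Severity is minor: the objective is secondary and descriptive, and the primary PFS analysis is untouched.

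**What to change.** In section 10.5.5.1, define the set as all patients randomized to rinse or standard of care in the sub-study, analysed by assigned group. Define the index episode as the one that triggered randomization, whatever adverse event term is recorded. For the duration from the adverse event CRF, use the same index episode and group stomatitis, oral mucositis and mouth ulcers.

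The cost is two or three sentences in section 10.5.5.1, carried into the analysis plan. No new data should be needed, because the randomization date should identify the episode. The recording instruction in section 6.2.2.1 can stay as it is.

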At the first onset of symptoms suggestive of stomatitis patients will contact the study site. Upon confirmation of stomatitis, patients in countries where the alcohol-free 0.5mg/5ml dexamethasone oral solution is commercially available will be randomly assigned to take either 0.5mg/5ml dexamethasone mouth rinse or the standard of care used to treat stomatitis at the patient's center. The mouth rinse will be self-administered at a dose of 10ml 3 times per day. Patients will be instructed to swish and expectorate the mouth rinse. Patients will also be instructed to fill out the Oral Stomatitis Daily Questionnaire (OSDQ) at home every day until the patient recovers. For subsequent episodes of stomatitis patients will be instructed to contact the physician. Upon telephone confirmation, they will be instructed to utilize the same treatment they were assigned to after the first episode and complete the OSDQ booklet. **Note:** only those patients who develop symptoms suggestive of stomatitis and who have the diagnosis of stomatitis confirmed by the study site will participate in the investigation of the stomatitis intervention. OSDQ will not be administered during the Extension Phase.

[figure not shown]

The primary analysis of PFS for first line treatment will be performed 12 months after the last patient's recruitment. The analysis of PFS for second line treatment will be performed 6 months later (18 months after the last patient's recruitment) provided that the number of patients in second line treatment is adequate for a reliable PFS analysis. Otherwise, this analysis will be performed 24 months after the last patient's recruitment. The overall survival analysis will be performed 24 months after the last patient's recruitment. Assuming an enrollment period of 18 months, the expected trial duration is therefore 42 months.

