	Category	Reference to Section	Screening/ Baseline	Cycles 1 cycle = 28 days*				End of treatment (EoT) for first line treatment	28 Day Safety Follow up*	Study Evaluation completion*	Survival follow up**	Post Treatment Evaluations
Cycle Number				C1	C2	C3	Subsequent cycles					
Visit Number			1	2	3	4	5,6,7...	777	501	778		
Day of cycle			-28 to -1	1	1	1	1	Last dose + ≤15 days	Last dose + 28 days			
Hepatitis screening and monitoring (if applicable)	D	7.2.2.5.4. 7.2.2.5.5.	X									
Urinalysis	D	7.2.2.5.6.	X	As clinically indicated								
Imaging:		7.2.1.										
CT or MRI for chest, abdomen, pelvis	D	7.2.1.	X			X	Every 8 weeks	X only for patients discontinuing for reasons other than documented PD, lost to follow up and death				X
CT or MRI for Brain	D	7.1.1.4.	X	As clinically indicated								
Bone scan or skeletal survey	D	7.2.1.	X			X	Every 8 weeks					
If baseline bone scan positive perform X-ray, CT or MRI	D	7.2.1.	X			X	Every 8 weeks	X only for patients discontinuing for reasons other than documented PD, lost to follow up and death				

	Category	Reference to Section	Screening/ Baseline	Cycles 1 cycle = 28 days*				End of treatment (EoT) for first line treatment	28 Day Safety Follow up*	Study Evaluation completion*	Survival follow up**	Post Treatment Evaluations
Cycle Number				C1	C2	C3	Subsequent cycles					
Visit Number			1	2	3	4	5,6,7...	777	501	778		
Day of cycle			-28 to -1	1	1	1	1	Last dose + ≤15 days	Last dose + 28 days			
Safety:			7.2.2.									
Adverse events	D	7.2.2.			Continuous during the study, up to 28 days after the last treatment				X			
Patient reported Outcomes – OSDQ		7.2.6.			Complete OSDQ daily during every episode of oral stomatitis.							
Everolimus administration	D	6.1.			Daily dosing							
Letrozole administration	D	6.1.			Daily dosing for FIRST LINE TREATMENT ONLY							
Study Evaluation Completion	D	7.1.6.1.							X			
Survival Follow-up	D	7.1.6.2.								X		
Antineoplastic therapies since discontinuation of study treatment	D	5.							X			X

	Category	Reference to Section	Screening/ Baseline	Cycles 1 cycle = 28 days*				End of treatment (EoT) for first line treatment	28 Day Safety Follow up*	Study Evaluation completion*	Survival follow up**	Post Treatment Evaluations
Cycle Number				C1	C2	C3	Subsequent cycles					
Visit Number			1	2	3	4	5,6,7...		777	501	778	

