## Other assessments

### 7.2.6 Patient reported outcomes

Patient reported outcome (PRO) and impact of oral stomatitis burden on patient's daily living will be evaluated using the Oral Stomatitis Daily Questionnaire (OSDQ). The PRO will be not be administered during the Extension Phase. Completion of the PRO questionnaire will be dependent on the availability of OSDQ in the local language. The OSDQ is a patient self-administered 6-item questionnaire with a 24-hour recall period. Sample of the questionnaires can be found in the [Appendix 1](#).

The OSDQ is an oral stomatitis-specific exploratory questionnaire developed for the purpose of this study. It is based on prior work by [Stiff et al \(2006\)](#) who developed and validated the Oral Mucositis Daily Questionnaire (OMDQ) to assess impact of oral mucositis on pain and daily functioning in patients undergoing autologous hematopoietic stem cell transplantation (HSCT). Although the OMDQ is available in the public domain (personal communication with the author, March 2012), it does not readily meet the need of this study as it contains diarrhea items more sensitive in measuring the symptoms intrinsic to the HSCT setting.

At the first episode of stomatitis, an OSDQ booklet will be handed out to patients at the study site upon confirmation of an oral stomatitis diagnosis. The booklet will contain 28 copies of the OSDQ, marked from Day 1 to Day 28, to be filled out by the patient up to 28 consecutive days, as long as the episode continues. During first episode of oral stomatitis, Day 1 OSDQ should be filled out on site by the patient. The patient should be given sufficient space and

time to complete the questionnaire. The site personnel should check the OSDQ for completeness and ask the patient to complete any missing responses but should not guide them in any way in their responses. Patient's refusal to complete all or any part of the Day 1 OSDQ should be documented in the study data capture system and should not be captured as a protocol deviation.

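### Daily mean severity from a diary that stops at recovery describes, on later days, only patients still symptomatic, not the severity burden of the two randomized stomatitis groups

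*Protocol*

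**What the plan says.** The secondary objective (Protocol Table 3-1) is to make stomatitis both less severe and shorter. Patients with confirmed stomatitis are randomized 1:1 to the dexamethasone rinse or to their centre's standard of care (6.3.2).

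Section 10.5.5.1 limits the analysis to one episode: "The analysis for this objective will be based on PRO data for the first incidence of" stomatitis. For severity, "The mean, standard deviation and 95% confidence interval of each severity items in the questionnaire will be calculated at each day" in each of the two groups and shown as a graph, with no test or contrast. For duration, "The duration of the first stomatitis incidence will be calculated using the dates reported in the PRO", and the median is estimated by Kaplan-Meier. A supportive duration analysis uses adverse event (AE) dates. An analysis of repeated episodes is exploratory and optional.

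Collection stops with the episode:

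- Section 4.1, and 6.1 in like terms, tells patients to "fill out the Oral Stomatitis Daily Questionnaire (OSDQ) at home every day until the patient recovers".
- Section 7.2.6 provides a 28-day booklet "to be filled out by the patient up to 28 consecutive days, as long as the episode continues".
- Tables 7-1 and 7-2 say "Complete OSDQ daily during every episode of oral stomatitis".

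Not every randomized patient will have diary data: "Completion of the PRO questionnaire will be dependent on the availability of OSDQ in the local language", and refusal is allowed for ("Patient's refusal to complete all or any part of the Day 1 OSDQ should be documented").

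In the Oral Stomatitis Daily Questionnaire (OSDQ, Appendix 1), a patient who answers 0 on soreness (item 3) is sent straight to item 5, so items 4a-e are blank that day.

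**The concern.** Two rules that are harmless separately combine badly. One averages by day; the other stops collecting when the patient recovers. On Day 1 every patient with a diary contributes. By Day 10 or 14 the mean is taken over those not yet healed, a group defined by outcome after randomization. If the rinse speeds healing, its group empties faster and its remaining patients may be the more severe or resistant cases. The randomized comparison is then lost on those days.

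A reader of the graph could see a smaller severity benefit than exists, none, or an apparent disadvantage, although total soreness was lower with the rinse. No other planned analysis fills the gap: Kaplan-Meier covers duration only, and the general AE severity tables are not set out as a first-episode comparison of these two groups.

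A smaller instance of the same fault lies in the skip rule. On a day with no soreness, items 4a-e drop out of their means instead of counting as no limitation.

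**Working it through.** The plan states no sample size, effect or expected value for this comparison, so there is no figure to reproduce. Every input below is an assumption chosen to show the range.

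**Inputs.**

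- Episode length is exponential with rate r = ln 2 / median. Medians are 10 days (standard of care, SOC) v 5 (rinse), then 10 v 7.
- Day 1 soreness (item 3) is 1/2/3/4 with probability 0.35/0.35/0.20/0.10, so its mean is 0.35 + 0.70 + 0.60 + 0.40 = 2.05.
- Where severe episodes heal more slowly, rates are multiplied by 1.5/1.0/0.7/0.5.
- In patterns (e) and (f) the rinse shortens only episodes with Day 1 soreness 1-2.

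**Formulas**, with t = day − 1 and p the probability of soreness s:

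- Share still symptomatic = Σ p·exp(−rt)
- Mean with recovered patients scored 0 = Σ p·s·exp(−rt) if soreness is constant, or Σ p·s·[exp(−rt) − rt·E1(rt)] if it falls linearly to 0 (E1 is the exponential integral)
- Diary-only mean = zero-scored mean / share symptomatic

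**One case in full: pattern (b), Day 10, 10 v 5 days.**

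- SOC: exp(−rt) = 0.392, 0.536, 0.646, 0.732. Share = 0.527, zero-scored mean = 1.19, diary-only mean = 1.193/0.527 = 2.26.
- Rinse: exp(−rt) = 0.154, 0.287, 0.418, 0.536. Share = 0.291, zero-scored mean = 0.72, diary-only mean = 0.720/0.291 = 2.47.
- Difference, rinse minus SOC: diary-only 2.47 − 2.26 = +0.21; zero-scored 0.72 − 1.19 = −0.47.

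**Day 10 difference (rinse minus SOC), diary-only / zero-scored:**

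| Pattern | 10 v 5 days | 10 v 7 days |
|---|---|---|
| (a) constant soreness, healing unrelated to severity | 0.00 / −0.51 | 0.00 / −0.26 |
| (b) constant, severe heals slower | +0.21 / −0.47 | +0.09 / −0.24 |
| (c) linear decline, severe heals slower | −0.19 / −0.34 | −0.10 / −0.19 |
| (d) linear decline, unrelated | −0.275 / −0.33 | −0.14 / −0.19 |
| (e) linear decline, rinse helps milder episodes only | +0.02 / −0.17 | −0.01 / −0.09 |
| (f) constant, rinse helps milder episodes only | +0.26 / −0.26 | +0.11 / −0.13 |

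**By day, 10 v 5.** The two versions of the difference are 0.07-0.14 apart on Day 2, 0.11-0.26 on Day 3 and 0.06-0.68 on Day 10. On Day 14, (d) gives −0.26 against −0.25, and (e) +0.07 against −0.13.

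**If the rinse also lowers soreness by 25% in (b)**, the Day 10 diary-only rinse mean is 0.75 × 2.47 = 1.85 against 2.26, so the display shows the rinse as better.

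**Numbers left, 10 v 5.** Still symptomatic on Day 10: 53-54% SOC v 29-36% rinse. On Day 14: 40-41% v 17-24%. By the binomial distribution with 10 per group, the chance that either group has at most one diary left, and so no SD or interval, is 8-18% on Day 10 and about 30-51% on Day 14. With 20 per group it is at most 1% and 3-14%. Final group sizes are not given.

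**The case against.** The strongest reply is that 10.5.5.1 names a statistic but no denominator, and that scoring of recovered days and skipped items is normally settled in the analysis plan, which is not shown. That plan could count recovered days as 0 and largely repair the display. This stands as a limit on the point. It does not remove it: the section fixes the statistic, the day, the episode and the groups, and other sections fix when entries stop. Following that text gives diary-only means.

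Second, severity while symptomatic, read beside Kaplan-Meier duration, is a coherent descriptive pair. This also stands. In pattern (a) the diary-only 0.00 is the right answer to that narrower question. Those means should therefore be kept and labelled, not removed.

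Third, the sizes are all assumed. On Day 10, clear reversal needs soreness that stays constant until it stops, as in (b) and (f). With declining soreness the result is attenuated, little changed or near zero. With 10 per group and 10 v 5 days, the standard error of the Day 10 diary-only difference under these patterns is 0.47-0.73, larger than any difference in the table, so neither display would settle the question at that size. The 20 randomized patients mentioned in the Amendment 4 rationale are a count at that date, not a stated final number.

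A reader might infer that the planned graph will hide or reverse a real benefit, or that the stomatitis objective fails. The documents support neither. They give no episode lengths and no relation between severity and healing, the early days are close to right, and faster healing is still credited in the duration analysis.

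**Conclusion.** The point holds in limited form. As written, the later-day severity means describe patients still symptomatic, and they can attenuate or miss a lower severity burden in the rinse group. Under some assumed patterns (soreness constant until it stops, with severe episodes healing more slowly or responding less) they reverse it. The gap from the zero-scored difference on Day 10 is 0.06 to 0.68 on a 0-4 item with medians of 10 v 5 days, and smaller with 10 v 7. These figures rest wholly on the assumed distributions.

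The display is secondary and descriptive, the protocol itself calls the questionnaire exploratory (7.2.6), and the primary progression-free survival analysis is untouched. The wording should be changed because the change is cheap and prevents a misreading, not because a trial conclusion depends on it.

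**What to change.** Change the wording of 10.5.5.1 only:

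1. Add a daily mean over randomized patients with OSDQ data. In it, items 3, 4a-e, 5 and 6 count as 0 on days after the last first-episode entry through Day 28, if item 3 = 0 on that entry. Failing that, they count as 0 from the AE end date, which is already collected (8.1.1). Never overwrite a recorded answer: a patient with item 3 = 0 still answers items 5 and 6 that day. Do not zero-score item 2, where 0 is the worst possible health.
2. Score items 4a-e as 0 on days when item 3 = 0.
3. Treat days as missing when the diary stops without recovery. Stop zero-scoring at the onset of a second episode before Day 28, and treat those days as missing.
4. Show for each day the number contributing and the number still symptomatic. Keep the diary-only means, labelled as severity while symptomatic.
5. Leave the Kaplan-Meier analysis from questionnaire dates and the supportive AE-date analysis as planned.

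No new data are needed. The cost is one of interpretation: the zero-scored mean mixes severity with duration and assumes no soreness after recovery, so it must be read beside the diary-only means and the duration analysis. Diaries that stop early lower the level. If 20% stop before recovery at the same rate in both groups under pattern (b), 10 v 5 days, the Day 10 means fall by 0.08-0.13 while the difference stays at −0.46 to −0.47. Unequal stopping between open-label groups is not covered by that check and remains a limitation.
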